9.6 Sampling

Sample Collection

The blood volumes that will be taken from each participant are detailed in the schedule of study assessments. The maximum blood volume to be taken per participant will be approximately 300ml, or 330ml for group 1, which is less than the volume of a single blood donation.

People who are blood donors can participate in FlaviPrime, but they cannot give blood concomitantly to the study. The maximum amount of blood that can be given in blood donation is 470 ml per 16 weeks. Therefore, a participant who is a blood donor cannot join FlaviPrime until 16 weeks after their last blood donation. Four weeks after the last FlaviPrime study sample is taken, the participant becomes is able to donate blood again.

Sample Shipment/Custodianship

Laboratory safety samples will be analysed at the Royal Liverpool University Hospital Laboratories. Experimental blood samples relating to the outcomes of this study will be analysed within the Department of Clinical Infection, Microbiology and Immunology, University of Liverpool. Samples will be transported from the CRU to the University of Liverpool in line with the study specific Material Transfer Agreement (MTA). Details of sample transport are in the bespoke laboratory manual for the study. Serological analyses will be performed in the laboratory of [name], Mahidol University, and Bangkok. Depending upon the initial results of the study, it may be beneficial to send samples to other laboratories, as is the case in the Acute emerging Virus Immunity Study.

Sample Storage and Handling

Samples given as part of the study, if they are not used in meeting the scientific objectives, will be stored for a period of 25 years. The samples can be used in future studies addressing the development of immunity to flaviviruses, and the cross-reactivity to flaviviruses, and to other emergent viruses, but not for other purposes (control antigens/mitogens will also be included). An example of such a use might be, testing for markers of immunity to a flavivirus or another virus that is undiscovered at the time of the study, but causes an outbreak in the future.

These samples would be used for the purposes as outlined above in section 7.3.1, although these may apply to other viruses. Permission to send material to other laboratories, and the parameters of the purpose of this, will be included in the consent form at the start of the study.

9.7 Intervention Discontinuation and Participant Discontinuation/Withdrawal

In consenting to the study, participants are consented to study treatment, follow-up and data collection. If voluntary withdrawal occurs, the participant should be asked to allow continuation of scheduled evaluations,

complete an end-of-study evaluation, and be given appropriate care under medical supervision until the symptoms of any adverse event resolve or the subject's condition becomes stable.

The critical study data in FlaviPrime is derived from experimental blood samples. Although participants can refuse a blood sample at any time, refusal to give crucial samples (weeks 1, 2 and 4 weeks post JE vaccine IMOJEV®) would result in significant compromise to the study. Therefore, any participant who does not give these samples for any reason will be replaced with a new volunteer and removed from the study sampling schedule thereafter. The participant will remain in the study for safety.

Premature Discontinuation of Study Intervention

Once the single dose of JE vaccine IMOJEV® has been given, there is, in practice, no intervention to be withdrawn from, and participants can remain in the study. Foreseeable reasons why a participant may withdraw from the study generally apply to the taking of study blood samples, and include:

- i. Participant withdraws consent
- ii. Participant is unable to attend regularly for assessment and to donate week 1, 2 and 4 post vaccination samples for any reason
- iii. Loss of capacity during the study
- iv. Any other change in the participant's condition that justifies the discontinuation of sample collection the study in the clinician's opinion.

A participant is free to withdraw from the study at any time. In addition, the CI may decide, for reasons of medical prudence, to withdraw a participant. In either event, the Sponsor will be notified and the date and reason(s) for the withdrawal will be documented in the participant's source data. If a participant withdraws or is withdrawn, ideally they should remain in the study for collection of safety data and/or treatment of any AEs, until these have resolved.

Participant Withdrawal from Follow Up

If a participant wishes to withdraw from the study sampling schedule, they will be informed by the CRU staff of the importance of remaining on study follow-up for safety, or failing this, of allowing routine follow-up data to be used for study purposes. Generally, follow-up will continue unless the participant explicitly also withdraws consent for follow-up. The CI may also request that the participant return for an additional follow-up visit, for the purpose of collecting safety data, or ensuring resolution/adequate treatment of an AE.

Participants are free to withdraw from follow up at any time without providing a reason, though a reason should be recorded if one is given. Those who wish to withdraw from further follow-up will have the data collected up to the point of that withdrawal included in the analyses. The participant will not contribute further data to the study and the CTU should be informed via email to the CTU and via completion of a Withdrawal CRF to be returned to the CTU within 7 days.

If participants express a wish to withdraw from follow up, the research team at site should ascertain if this is for all elements of study follow-up, or if for example data from routine assessments can still be collected for the study. In the case of ongoing adverse events, participants should be given appropriate care under medical supervision until the symptoms of any adverse event resolve or the participant's condition becomes stable.

Any SAEs will be notifiable to the CTU via processes detailed in Section 11 even if a participant has withdrawn from follow up.

Participant Withdrawal from Study Completely

Participants who withdraw from the study for other reasons have previously consented to follow-up in the study. Data up to this time can be included in the study if anonymised. They may need to reaffirm that they consent to follow-up through usual NHS mechanisms. If the participant explicitly states their wish not to contribute further data to the study, a withdrawal CRF should be completed.

Participant Transfer

For participants moving from the area, every effort should be made to encourage the participant to continue to attend follow-up if possible. If this is not possible, the participant will have to be withdrawn from the study. If the participant is withdrawn before the day 9 sample (group 1) / two-week sample (groups 2 and 3) has been donated, the participant should be replaced if possible (dependent on the availability of vaccine). This should be discussed with the Chief Investigator and LCTC.

Loss to Follow-up

If for any reason a participant does not complete the study they should attend a final visit / assessment with the study clinician as soon as possible. If the study treatment is stopped before the end of the scheduled assessment period, the clinician may contact the participant to request additional information up to the point where the study treatment would be complete.

Travel

Participants in the study will be required not to travel to a JEV and DENV endemic area until the sampling schedule has reached study week (SW) 8.

If any participant who does travel to a JEV and DENV endemic area before 8 weeks, consideration will be given to replacing them by the study oversight committee. They will remain in AVIS to gather additional data. For example, a participant who contracted a wild type flavivirus infection during the study would represent a natural experiment of great relevance to the principles under investigation in this study.

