Each group will receive a single dose of live JE vaccine IMOJEV®. All doses will be administered at the LUHFT CRU facility in accordance with a bespoke vaccination administration working instruction. Group 1 participants will be in the study for 28 days and will give 6 blood samples, one on the day vaccination and then daily on days 5 through to 9 post vaccination. Group 2 and 3 participants will be in the study for a total of 8 weeks and will be expected to attend study visits and provide six blood samples at baseline, and weeks 1, 2, 4, and 8 (see Figure 2, Study Schedule). All participants will have Adverse Events (AEs) recorded while they are in the study. Sample collection in the Acute emerging Virus Immunity study (AVIS) will be temporarily suspended during FlaviPrime, participants will then revert back to AVIS once the FlaviPrime sampling collection period has finished. Participants will be followed up, aiming for 5 years of follow up, and have already been consented for storage of contact details for future studies.

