10.6 Time Period for Active Monitoring of Safety Events

IMPORTANT: Any safety events occurring after the end of the below described “active monitoring” period which meet the definition of serious and are recorded for this study must continue to be reported by sites to the LCTC in accordance with the timeframes and procedures described in section 11.3. The same processes established for SAEs within the active monitoring period should be followed for these events.

All new serious adverse events should be reported from the point of consent until 28 days after administration of the study vaccine. Depending on the nature of the event, the reporting procedures below should be followed. Any questions concerning adverse event reporting should be directed to LCTC in the first instance. Group 1 participants, who have their last study visit 9 days after vaccination, will be encouraged to report any adverse events that occur up to 28 days to the LUHFT CRU by phone.

AEs that occur during this timeframe should be reported to LCTC via the AE form. When reporting an increase in severity for an existing AE, the AE form should be changed to the new grade and the reason why (increase in severity) included. For a decrease in severity, no action is to be taken unless the symptoms have fully resolved (in which case the AE/SAE should be updated until resolved).

Although the period of adverse event monitoring in this study is 28 days, if the site team become aware of an adverse event that occurs outside this time and there are reasonable grounds to suspect the event is related to the vaccine or to participation in the study, it would be good practice to report this event to LCTC.

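### Section 9.7 gives opposite instructions for a vaccinated participant who moves away: withdrawal from the study, or retention for safety follow-up

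*Protocol*

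**What the plan says.** Every participant receives one vaccination, given at baseline: "Each group will receive a single dose of live JE vaccine IMOJEV" (section 5; timing in 9.5). Section 10.6 sets the safety period: "All new serious adverse events should be reported from the point of consent until 28 days after administration of the study vaccine". It applies the same 28 days to adverse events in general.

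Section 9.7 then deals several times with participants who stop attending:

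- **Opening text.** A participant who does not give the crucial samples (weeks 1, 2 and 4), whatever the cause, is replaced and leaves the sampling schedule, but "The participant will remain in the study for safety".
- **Premature Discontinuation of Study Intervention.** After the dose "there is, in practice, no intervention to be withdrawn from, and participants can remain in the study". Being unable to attend is listed as a foreseeable reason for withdrawal. Someone who withdraws or is withdrawn should *ideally* stay for safety data.
- **Participant Withdrawal from Follow Up.** Follow-up generally continues unless consent for it is explicitly withdrawn. Serious adverse events remain notifiable even after withdrawal from follow-up.
- **Participant Transfer.** For someone who moves, continued attendance is encouraged. "If this is not possible, the participant will have to be withdrawn from the study".
- **Loss to Follow-up.** Anyone who does not complete is asked for a last attendance: "they should attend a final visit / assessment with the study clinician as soon as possible". The next sentence begins "If the study treatment is stopped before the end of the scheduled assessment period" and continues that "the clinician may contact the participant to request additional information up to the point where the study treatment would be complete".

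**The concern.** The transfer rule and the opening rule are both mandatory, and they give the same person opposite statuses. The mover has not refused follow-up and has already been vaccinated; the withdrawal is imposed because visits are no longer practicable. A site that applies the transfer paragraph literally could stop collecting safety information while the 28-day period is still running.

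At stake is the completeness of non-serious adverse event data. Section 9.8 (Study Discontinuation) includes a scenario based on clinically relevant symptoms or intolerable events of a similar nature in two or more participants. Those events need not be serious, so continued notification of serious events does not fully protect that scenario. Section 11.3 (Safety Reports) also reports events by participant group, and the groups are small.

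**Working it through.** The plan states no figure on this point, so there is none to reproduce. The check compares the passages and makes one subtraction.

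**Inputs**

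- Safety period: 28 days after vaccination (10.6).
- Group 2 and 3 visits after vaccination: days 7 (±1), 14 (±2), 28 (±3) and 56 (±7) (9.5, Schedule of Assessments).
- Crucial samples: weeks 1, 2 and 4 (9.7).
- Telephone reporting to day 28: described for Group 1, whose last visit is day 9 (10.6).
- Group sizes: 6–10 in Group 2, 8–12 in Group 3 (12.2).

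**Step 1: a test case.** A Group 2 participant attends on day 7, moves away on day 10 and cannot return.

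| Rule in 9.7 | Triggered? | Status it gives |
|---|---|---|
| Opening text, crucial samples | Yes: weeks 2 and 4 are missed | Off sampling, stays in the study for safety |
| Participant Transfer | Yes: moved, cannot attend | Withdrawn from the study |
| Withdraws or is withdrawn | Yes, if the transfer rule is applied | *Ideally* stays for safety data |
| Withdrawal from Follow Up | Default applies: consent not withdrawn | Follow-up generally continues |

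The first two rows are mandatory and incompatible.

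**Step 2: does other text decide between them?** The *ideally* sentence is weaker than the opening rule and does not say which rule governs. The default on follow-up points towards retention but does not mention transfer. The final visit under Loss to Follow-up requires attendance, which is what the mover cannot do. The telephone route in 10.6 is written for Group 1 only. The conflict therefore stays open for Groups 2 and 3.

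**Step 3: days at risk.** Uncovered days = 28 − d, where d is the day of the last attended visit.

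- d = 7: 28 − 7 = 21 days (21/28 = 75%); 20 to 22 days across the ±1 visit tolerance.
- d = 14: 28 − 14 = 14 days (14/28 = 50%); 12 to 16 days across the ±2 tolerance.
- Once the week 4 sample has been given, at the earliest on day 25, at most 28 − 25 = 3 days remain, and the crucial-sample rule is no longer triggered.

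**Step 4: weight of one participant.** Group 2: 1/10 to 1/6 = 10% to 17%. Group 3: 1/12 to 1/8 = 8% to 13%.

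**Step 5: the Loss to Follow-up sentence.** Its condition is that treatment is stopped early. After a single dose, 9.7 itself says there is in practice nothing to withdraw from. The condition is not met after vaccination, so the end-point in the sentence is never reached.

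**The case against.** The strongest reply is that safety follow-up is already protected. The opening rule covers missed crucial samples whatever the cause, so a Group 2 or 3 participant who moves before the week 4 visit falls under it. Follow-up continues by default, serious events stay notifiable, and reporting to day 28 does not depend on attendance. The protocol also accepts spontaneous reports (9.5) and events learned of by other means (11.1). Inclusion criterion 3 excludes planned relocation, so the case should be rare.

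Most of this stands, and it limits the point to non-serious events in an unplanned mover. It does not remove the contradiction. The transfer paragraph addresses this situation specifically and prescribes the opposite outcome, and the entry for 9.7 in section 17.4 shows that withdrawal was a deliberate clarification. A duty to report serious events also provides no means of learning about them from someone no longer seen.

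Two stronger readings are tempting and are not supported:

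- **A contact window of 0 of 28 days.** A reader might infer this because treatment is complete on the day of the dose. The sentence is permissive (*may*), does not forbid later contact, and depends on a condition that does not arise after the dose.
- **A loss of 28 − 9 = 19 days.** Day 9 is Group 1's last visit. A Group 1 participant who moves after it has no visit left to miss and already has the telephone route. The figure cannot be carried over to Groups 2 and 3, whose visit days differ.

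**Conclusion.** The point holds as an internal contradiction within 9.7, with a consequence for the 28-day period in 10.6. For a Group 2 or 3 participant who moves before the week 4 visit, safety status is undetermined. Non-serious adverse events may go uncollected for up to 21 days (last visit day 7) or 14 days (last visit day 14).

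This rests on three assumptions: the participant attended at least the week 1 visit, visits fall on their nominal days, and missing any one crucial sample triggers the opening rule. The figures are upper bounds, because they suppose that a site applies the transfer rule literally and that nothing is reported spontaneously.

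The documents do not show that the protocol ends safety data early for all who move or are lost. No sample size or planned analysis figure is affected. The matter is small but worth correcting, since the data concerned can bear on the scenario in 9.8 that counts two or more participants.

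**What to change.** Reconcile 9.7 with itself and with 10.6:

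1. **9.7, Participant Transfer.** State that a participant who moves and cannot attend is withdrawn from the sampling schedule and stays in the study for safety, in line with the opening text of 9.7.
2. **10.6.** Extend the telephone route now described for Group 1 to these Group 2 and 3 participants until the end of the stated 28-day period, unless consent for follow-up is withdrawn.
3. **9.7, general sentence on those who withdraw or are withdrawn.** Make clear that *ideally* does not weaken the rule for participants who have not withdrawn consent for follow-up.
4. **9.7, Loss to Follow-up.** At the same time, tidy the treatment-stopped sentence, which has no function in a single-dose study, so that it refers to the safety period in 10.6.

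The cost is a few phrases in an amendment and an occasional telephone call. No visits or samples are added.

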9.8 End of Study

The end of the study is defined to be the date on which data for all participants is frozen and data entry privileges are withdrawn from the study database (database is locked). Study enrolment may be stopped at a site when the total requested number of participants for the study have been recruited. The Study Oversight Committee may recommend that the study be stopped prematurely. In such circumstances of premature termination / suspension of the study, National Research Ethics Service (NRES) and HRA will be notified according to standard reporting guidelines

Site and closure activities will be centrally coordinated and conducted in accordance with CTU processes regardless of whether the study closes as planned or prematurely. This includes activities such as:

- End of Study notification to REC
- Study-related materials reconciled and returned/disposed of as appropriate see section 7.5 for IMP
- All site data entered onto the study database, discrepancies raised and satisfactory responses received

- Quality Control checks of the Investigator Site Files, Pharmacy Files and Study Master File as appropriate.

Study Discontinuation

If this study is prematurely discontinued (e.g., due to safety) all participants must be informed and the reason for the discontinuation should be written on the end of study form for each participant. If a participant has been withdrawn completely from the study whilst it is still ongoing, an end of study form should be completed.

The need for stopping the study will be considered by the study Oversight Committee. The decision will be based upon participant safety. If any of the following scenarios occur with reasonable possibility of a causal relationship with the study vaccine, no further doses of study vaccine will be given.

1. Clinically relevant signs or symptoms or intolerable adverse events of similar nature occurring in 2 or more participants that in the opinion of the CI warrant stopping,
2. One or more participants report a serious adverse event considered by the CI, local PI, or delegated other physician who can assess causality and expectedness of AEs to be at least possibly related to the study drug.

10 SAFETY REPORTING

Safety reporting in clinical trials is a legal and ethical requirement and it is imperative that all applicable requirements detailed here are followed during the study.

10.1 Terms and Definitions

Adverse Event (AE)

Any untoward medical occurrence, unintended disease or injury or any untoward clinical signs (including an abnormal laboratory finding) in subjects, users or other persons whether or not related to the study vaccine.

Related Adverse Event (Related AE)

An AE which resulted from administration of any of the research procedures – i.e. assessed as “probably”, “possibly” or “almost certainly” related to the study procedures or vaccine (see section 7)

Related Unexpected Adverse Event (RUAE)

A Related AE which is not expected, i.e. not consistent with the known effects of the study vaccine or research procedures (see section 7).

Serious Adverse Event (SAE)

An adverse event which meets the definition of “serious” (see section 10.2).

Related Serious Adverse Event (Related SAE)

A SAE which is assessed to be “probably”, “possibly” or “almost certainly” related to the study vaccine or study trial procedures (see section 7).

Related Unexpected Serious Adverse Event (RUSAE)

A Related SAE which is not expected, i.e. not consistent with the known effects of the study vaccine or study trial procedures (see section 7).

Reference Safety Information (RSI)

The information used for assessing whether an adverse reaction is expected (see section 10.5). This is contained in the Investigators Brochure (IB) for the vaccine. The RSI used to assess the expectedness of a SAE/SAR must be the current approved version at the time of onset of the SAR. The RSI for this trial is defined in section 10.5.

10.2 Assessment of Seriousness

The assessment of seriousness of safety events should be performed by an appropriately delegated, medically qualified member of the site research team.

A #safety event (whether or not assessed as related to the study) is assessed as serious if it:

- Results in death;
- Is life-threatening (i.e. the investigator considers the event places the subject at immediate risk of death from the experience as it occurred (this does not include an adverse experience that, had it occurred in a more severe form, might have caused death);
- Requires hospitalisation or prolongation of existing hospitalisation (hospitalisation is defined as an inpatient admission, regardless of length of stay, even if the hospitalisation is a precautionary measure for continued observation);
- Results in persistent or significant disability or incapacity (substantial disruption of one's ability to conduct normal life functions);
- Consists of a congenital anomaly or birth defect (in offspring of study participants, or their partners, regardless of time of diagnosis), or

- Is otherwise considered medically significant by the investigator.

#safety event / reaction applies apply to either AEs, or ARs, or Related AEs,

